## **11.0 Privacy/Confidentiality Issues**

We will use the web-based Vanderbilt Research Electronic Data Capture (REDCap) system to design electronic data-collection forms in all Aims. These forms will be pilot tested before use. Data will be input into a protected, web-based case report form (which can be readily downloaded into SAS, STATA, R, or SPSS). The form allows for direct data entry by investigators and is designed to minimize errors and erroneous values. Expected ranges are pre-specified to prevent errors such as the shifting of decimal points. The program includes a computerized audit trail so that the identity of individuals entering or changing data and, in the case of changes, both original and revised data are saved. Data are backed up daily.

A unique identification case number will be used to protect the confidentiality of the study participants. Only case numbers will be included in spreadsheets used for the statistical analysis.

## **12.0 Follow-up and Record Retention**

All research records will be accessible for inspection and copying by authorized representatives of the IRB, federal regulatory agency representatives, and the department or agency supporting the research. All study documents will be retained for at least six years after the closure of the study with the IRB.

## Appendix A Summary of study procedures

	+/-3 days						+/-4days				
	Day-7	Day -1	Day 0	Day 1	Day 3	Day 13	Day 14	Day 15	Day 17	Day 29	Day 43
CRC visit			X				X				
HD visit	X	X		X	X	X		X	X	X	X
Blood draw PK		X		X	X			X	X	X	X
Blood draw clinical labs	X				X	X			X	X	
Blood draw research labs		X		X				X			X
Serum pregnancy test			X				X				
Drug administration			X				X				
Medical history /PE			X								
QOL questionnaire/ recovery time			X				X				X
Symptoms questionnaire/ BP monitoring log				X	X			X	X	X	X
NIRS		X						X		X	X
Physical performance tests - Body composition***			X				X				X***
Collect dialyzer		X		X	X			X	X	X	X
activity monitor*	X*										X*

\* monitor ends after at least 5 days of consecutive use

\*\*It includes: physical performance tests (six-minute walk test, physical battery, and handgrip strength), bioelectrical impedance analysis, and MUAMC

\*\*\*Physical performance will only include handgrip strength

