The next two consecutive dialysis treatments after each drug administration (days 1 and 3, and days 15 and 17), we will conduct follow-up visits at the dialysis unit to collect information regarding symptoms after discharge from the CRC. During these visits, at the end of every hemodialysis session, we will also inquire, through a standardized questionnaire, about the presence of any symptoms associated with hypotension. This questionnaire will include symptoms such as cramps, dizziness, nausea, and will be scored according to the severity from 0 to 4 (none to severe). We will also collect blood samples at the dialysis unit for pharmacokinetics and special laboratory analysis. During the six-week length of the study, we will monitor the occurrence of DIH episodes and changes in blood pressure in every dialysis session. For this purpose, we will use the dialysis clinic blood pressure monitor logs. We will also conduct two additional visits at the dialysis units (Day 29 and 43) to draw blood, administer the symptomatology questionnaire, and measure blood flow with NIRS. In the final hemodialysis visit (day 43) we will also give the patients an activity monitor that will be collected after five consecutive days of continuous use. During this last visit, we will also administer the QOL questionnaire, obtain the dialysis recovery time, and perform body composition and physical performance tests (except for the six-minute walk test). Details of the study protocol can be found in Figure 5, Tables 1 and 2, and Appendix 1

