### **Collection of blood samples**

Blood samples will be collected for clinical laboratory analysis in the pre-dialysis blood sample. Blood samples at the dialysis unit will also be obtained at the arterial and venous sites before dialysis, 15 minutes and one hour after dialysis initiation, and at the end of hemodialysis for research labs (e.g., markers of the kallikrein-kinin system) and pharmacokinetics analysis.

Table 1. HD study visit

• Activity monitor (Day -7 and 43)

• NIRS (Days -1, 15, 29, and 43)

• Symptomatology questionnaire

• Blood draw at the venous and arterial sites: t=0, t=15min, t=1h, t=end of HD for markers of kallikrein-kinin system and PK

----------------------------------------------------------------------------------------------------------------------------------------------------------------------------------------------------------------------------------------------------------------------------------------------------------------

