## **7.0 Risks**

### ***a. Risks to human subjects***

1. Redness, swelling, burning, rash, or discomfort may occur at the site of the lanadelumab injection. Should this occur we will put ice on the site.
2. Lanadelumab may increase the risk of upper respiratory infections. Cold symptoms such as runny nose, sore throat, and sneezing are commonly observed. We will closely monitor the occurrence of those symptoms, and if necessary, we will stop the study.
3. Other side effects of lanadelumab include headache, muscle pain, and diarrhea. These side effects are uncommon but will be monitored during the study. If any of them persist, the patient will be withdrawn from the study.
4. Lanadelumab may induce elevation of transaminases, which is rare and transient. We will closely monitor the transaminase levels, particularly after the administration of the study drugs.
5. Lanadelumab may pose unforeseeable risks to the subject, an embryo or fetus, or a pregnant woman. Pregnant women are excluded.
6. Should new information become available during the study that may influence a subject's willingness to participate, we will make that information available and amend the consent form appropriately.
7. The collection and storage of DNA for genotyping creates the risk of release of information that could link subjects to stored samples and genotyping results.

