- Serum electrolytes will be measured before study visits in blood draws for clinical labs (See Appendix A). Also, we will monitor potassium levels using the monthly labs obtained in the hemodialysis unit. For serum potassium from 5.5-5.9 mmol/L, the dietary restriction will be emphasized, and the potassium content of the dialysate will be adjusted to decrease serum potassium. Predialysis serum potassium of 6.0-6.4 mmol/L, if confirmed and not corrected with adjustment of dialysate potassium concentration, will result in discontinuation of the study. Confirmed predialysis serum potassium of 6.5 mmol/L or greater will result in immediate discontinuation. All potassium measurements will be obtained before dialysis.
- Transaminases levels will be monitor after the administration of the first study drug. If the levels increase four times the upper limit of normal the patient will be excluded from the study and will not receive the second dose of the study drug.

Also, if the levels of the transaminases do not return to normal within one week after the elevation, the patient will not receive the second dose and will be excluded from the study.

- There are many safeguards in place to prevent the release of information from this study. All research samples are coded with the subject's unique identifier. Data sets used for the analysis also only contain this identifier. The key to the code is protected. Only the investigator, co-investigators, and research nurse have access to information that identifies subjects as participating in the study. The results of tests run on research samples will not be recorded in any subject's medical record, and neither the subject nor his or her doctor will be told of the results, except in the case of unsuspected significant arrhythmia or myocardial infarction. Access to the Vanderbilt computer network is protected at the level of firewalls, TCP wrappers, and University assigned user IDs. Data are secured with encryption algorithms, and the network is maintained by the Medical Center's Network Computer Service.

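### The last scheduled clinical labs fall at nominal Day 29, so a late asymptomatic transaminase rise in a completer has no scheduled follow-up, although blood is drawn at Day 43 anyway

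*Combined protocol and SAP*

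**What the plan says.** Section 7.0 (Risks to human subjects) lists the liver signal and a commitment: "Lanadelumab may induce elevation of transaminases, which is rare and transient", followed by "We will closely monitor the transaminase levels, particularly after the administration of the study drugs". No sampling days are given there.

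Section 8.0 (Protection against risk) holds the working rules. It opens the transaminase item with "Transaminases levels will be monitor after the administration of the first study drug". Two stopping conditions follow: a rise to four times the upper normal limit, or a rise that has not settled after a week. Both end with the patient leaving the study without dose 2. The same section places electrolytes in the scheduled draws ("Serum electrolytes will be measured before study visits in blood draws for clinical labs (See Appendix A") and adds a second source for one analyte only: "we will monitor potassium levels using the monthly labs obtained in the hemodialysis unit".

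Appendix A marks "Blood draw clinical labs" on Days -7, 3, 13, 17 and 29. The Day 43 cell is blank in that row but marked in the PK and research-lab rows. Section 6.0 (Study protocol) agrees that blood is taken at the last visit: "We will also conduct two additional visits at the dialysis units (Day 29 and 43) to draw blood". Section 6.0 (Collection of blood samples) says when the clinical specimen is taken: "Blood samples will be collected for clinical laboratory analysis in the pre-dialysis blood sample".

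Section 9.0 provides for withdrawn subjects to be treated or followed until their symptoms resolve.

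**The concern.** Transaminase elevation is a laboratory finding and often has no symptoms, so it is seen only if blood is tested. After dose 1 the protocol says what to do with such a finding. After dose 2, when the subject has had the full regimen, it gives no threshold, no recheck interval and no follow-up instruction, and scheduled testing ends at Day 29 while the subject stays on study to Day 43.

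Two things are at stake, both small. A rise first seen at Day 29 may never be documented as resolved, and a rise that begins later may not be seen at all. The late safety record for a named drug risk would then be incomplete, although a tube could be added at a draw that already takes place.

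**Working it through.** The plan states no figure on this point, so there is none to reproduce. The check is a reading of the schedule plus day arithmetic.

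**Inputs**
- Dose 1 on Day 0 and dose 2 on Day 14 (Section 6.0, Study protocol; Appendix A).
- Clinical labs on Days -7, 3, 13, 17 and 29 (Appendix A).
- PK blood on Days -1, 1, 3, 15, 17, 29 and 43; research blood on Days -1, 1, 15 and 43 (Appendix A). Each of the three blood-draw rows has one label and 11 day cells, so the columns line up.
- 16 subjects per arm (Section 10.0, Sample size).

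**Nominal days**
- After dose 1: labs at 3 - 0 = 3 and 13 - 0 = 13 days.
- After dose 2: labs at 17 - 14 = 3 and 29 - 14 = 15 days.
- Final visit: 43 - 14 = 29 days after dose 2.
- Stretch with no scheduled clinical lab: 43 - 29 = 14 days.

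**Effect of the visit windows.** The Appendix A header shows +/-3 days above the Day -7 column and +/-4 days above the Day 14 column. If these are merged headers, as the layout suggests, the +/-4 days applies from Day 14 onward. With dose 2 held on Day 14, the Day 29 lab could fall from 25 - 14 = 11 to 33 - 14 = 19 days after it. The counts above are therefore nominal.

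**Does any other provision cover the late period?**

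| Provision | Does it schedule a transaminase test on or after Day 29? |
|---|---|
| Section 8.0, transaminase rules | No. They govern the time after dose 1 and whether dose 2 is given. |
| Section 8.0, monthly dialysis-unit labs | No. They are cited for potassium only. |
| Section 8.0, Data and Safety Monitoring Plan | No. It covers reporting of events and toxicities, not repeat samples. |
| Section 9.0, withdrawal | No. It concerns withdrawn subjects and is tied to symptoms, with no lab schedule. |
| Appendix A, Day 29 | Yes, if the clinical panel includes transaminases. This is the last one. |
| Appendix A, Day 43 | No clinical labs, although other blood is drawn. |

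The case left uncovered is a subject who completes the study and has an asymptomatic rise at Day 29 or later.

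**What each part of a remedy would do.** A Day 43 lab gives a value nominally 14 days after Day 29. That is longer than the one-week interval the protocol uses after dose 1, so it detects later rises but is not by itself a one-week recheck. A recheck rule deals with a Day 29 rise. It also deals with a Day 17 rise, which would otherwise next be tested 29 - 17 = 12 days later. The two parts do different jobs.

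**The case against.** The strongest reply is that the plan already does what it promises. Two labs are scheduled after each dose, the protocol itself regards the elevation as uncommon and self-limiting, and the principal investigator is responsible for safety. Subjects dialyse three times a week, which gives about 3 x 2 = 6 sessions between Days 29 and 43 at which a repeat could be ordered. Section 9.0 also lets a non-transient adverse event lead to withdrawal and follow-up. On this view an extra tube is a matter of preference.

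Most of that stands, and it is why the point ranks low. What it does not supply is a written instruction: an unscheduled repeat is possible but nowhere requested, and Section 9.0 follows symptoms, which an asymptomatic rise lacks.

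Three stronger readings are tempting and should be resisted.
- A reader might infer that the Section 7.0 commitment is broken. It names no days, and the labs on Days 17 and 29 are monitoring after dose 2.
- A reader might infer that the one-week rule after dose 1 cannot be met on schedule, because labs fall on Days 3 and 13. The visit window may allow the second of these to be taken on Day 10, so the documents do not establish this.
- A reader might try to size the late risk from the drug's half-life or from an assumed event rate. The documents give no rate for late elevations, and drug level is not a measure of liver risk.

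**Conclusion.** The point holds as an optional, low-cost improvement to the safety schedule. Clinical labs stop at nominal Day 29, about 15 days after dose 2, and the remaining 14 nominal days to the final visit have none. An asymptomatic transaminase rise found on or after Day 29 in a completer has no scheduled follow-up.

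The conclusion rests on two assumptions. The first is that transaminases are part of the clinical panel and of no other Day 43 assay. The panel is not itemised, but no other scheduled draw is a reasonable place for them. The second is that the table's columns were read correctly, which the text on the Day 43 draw supports.

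The number of subjects affected cannot be estimated from the documents and is probably very small. The gain is limited to a late safety value or a documented return to normal. The primary analysis, the efficacy endpoints and the decision to give dose 2 are untouched.

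**What to change.** 1. In Appendix A, mark clinical labs at Day 43 and state that the panel includes transaminases. Use the pre-dialysis blood already being drawn at that visit.
2. In Section 8.0 (Protection against risk), add one sentence: a transaminase elevation found after dose 2 will be rechecked within one week at a regular dialysis session and followed until normal. Say that this also applies to a rise first seen at Day 43, where the recheck falls after the last study visit.

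**Cost.** One extra chemistry tube per subject, 2 x 16 = 32 in all. Subjects who drop out and are replaced before Day 43 add none. No visit or needle stick is added on schedule, and recheck tubes are needed only if an elevation is found.

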## 2.0 Rationale and Specific Aims

### A. Specific Aims

In **Specific Aim 1** we will test the hypothesis that **in patients with DIH, inhibition of plasma kallikrein system with lanadelumab prevents the reduction of blood pressure and maintains hemodynamic stability**. For this purpose, we will monitor heart rate and blood pressure during hemodialysis. Importantly, we will conduct the study in an outpatient clinic, using the patients' usual hemodialysis dose and settings as for a regular hemodialysis session. This approach will minimize the risk that our findings were biased by conducting the study in a clinical research setting.

In **Specific Aim 2** we will test the hypothesis that **in patients with DIH, inhibition of plasma kallikrein system with lanadelumab prevents symptoms associated with DIH such as cramps, dizziness, and nausea and improve recovery time after hemodialysis**. Hemodialysis is associated with many complications, including DIH, that negatively affect the QOL of patients and their families. Any intervention that prevents the occurrence of DIH will result in a faster recovery from hemodialysis. The present study will evaluate the impact of lanadelumab on preventing symptoms associated with DIH and reducing recovery time after hemodialysis.

**Figure 3.** Effect of one- week treatment with ramipril or placebo on bradykinin concentrations in response to hemodialysis

[figure not shown]

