## 6.0 Study Procedures

### Study protocol

After obtaining consent, study subjects will undergo the following procedures.

**COVID-19 precautions prior to and during visits.** Pre-visit phone call – we will contact the patient before all of their study visits to ask a series of COVID-19-related screening questions. Depending on their answers, we will continue with the study visit or postpone for another time. The patient will be asked to wear a face covering during all portions of their study visits in which they are in the presence of hospital staff. We will also encourage frequent hand washing and/or provide alcohol-based hand sanitizer.

Subjects will participate in a randomized, parallel-group, double-blind, placebo-controlled study in which they will receive two doses of placebo or 300 mg of lanadelumab subcutaneously. Participants will continue their usual medications throughout the study. One week (Day -7) before the administration of the first dose of the study drug, we will conduct a study visit at the hemodialysis unit. During this visit, we will give the participants a physical activity monitor to be worn for at least 5 consecutive days and will obtain baseline blood samples. During a second study visit at the dialysis unit (Day -1), we would obtain a second baseline blood sample one to three days before the administration of the first dose of the study drug. In this visit, we will also measure

muscle oxygenation using near-infrared spectroscopy (NIRS). Patients will be then asked to come to the Vanderbilt Clinical Research Center (CRC) on a non-dialysis day. During this visit (Day 0), we will obtain a detailed history, perform a physical examination, administer a quality of life (QOL) questionnaire, obtain the dialysis recovery time, and evaluate body composition and physical performance. We will then administer the first dose of the study drug and monitor the appearance of any Type I (immediate) hypersensitivity reaction for two hours before discharging patients from the CRC. We will repeat the same protocol, as outlined for Day 0 and administer the second dose of the study drug two weeks later at the CRC (Day 14).

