## **10.0 Statistical Considerations**

### ***a. Sample size***

The primary outcome will be the change in blood pressure during hemodialysis. For this, we will average blood pressure during hemodialysis of three hemodialysis sessions within the second week of treatment. Secondary endpoints will also be recorded during the second week of treatment and will include the number of hypotensive events, frequency of nursing interventions, average of dialysis recovery times, and average symptoms severity score. Based on our preliminary studies with icatibant and assuming a standard deviation of differences of 13.6 mmHg (pooled SD of the delta), a sample size of 16 in each arm will have 80% power to detect a difference in means of -13.7 mmHg, using a paired t-test with a 0.05 two-sided significance level.

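### The symptom severity score, a secondary endpoint under Aim 2, has no designated pre-dose baseline although two pre-dose dialysis visits already exist; the cost is precision, not bias

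*Combined protocol and SAP*

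**What the plan says.** Aim 2 (Section 2.0) is the hypothesis that lanadelumab "prevents symptoms associated with DIH such as cramps, dizziness, and nausea and improve recovery time after hemodialysis". Section 10.0a makes the "average symptoms severity score" a secondary endpoint, taken from the second week of treatment. Each symptom is scored 0 to 4.

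The schedule appears in three places:

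- **Appendix A.** The row "Symptoms questionnaire/ BP monitoring log" is ticked on Days 1, 3, 15, 17, 29 and 43. It is blank on Days -7, -1 and 13, all of which are marked as dialysis visits.
- **Section 6.0, Study protocol.** On Day -7 "we will give the participants a physical activity monitor to be worn for at least 5 consecutive days and will obtain baseline blood samples". For the other pre-dose dialysis visit the text reads "During a second study visit at the dialysis unit (Day -1), we would obtain a second baseline blood sample", and muscle oxygenation (NIRS) is added. The questionnaire first appears at the visits after each dose and again on Days 29 and 43.
- **Table 1 (dialysis study visit).** "Symptomatology questionnaire" is listed with no days, whereas the activity monitor and NIRS lines carry days.

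Recovery time, the other half of Aim 2, is obtained on Day 0 before the first injection. Section 10.0b plans a paired t-test of lanadelumab against placebo for the secondary endpoints and names no baseline covariate.

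**The concern.** Symptom burden differs between patients and probably persists to some degree within a patient. A pre-dose score would let the analysis remove that stable part from the treatment comparison. In a trial of 16 per arm, with permuted blocks and no stratification factor named in Section 5.0, that gain is worth having. The plan collects pre-dose values for recovery time, quality of life, physical performance, NIRS and activity, and gives no reason for leaving out the symptom score. Without a designated pre-dose score, neither baseline adjustment nor a change from baseline is defined for this endpoint.

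**Working it through.** **1. The plan's own figure.** Section 10.0a gives 16 per arm for blood pressure: difference 13.7 mmHg, SD 13.6 mmHg, two-sided 0.05, 80% power.

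- Two-group formula: n = 2 × (1.960 + 0.842)² × (13.6/13.7)² = 15.47, so 16 per arm. Power at 16 is 81.3% (normal) or 78.7% (t).
- The paired t-test named there would need only 10 pairs (80.9%), and 16 pairs would give 96.4%.

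The stated size is therefore a two-arm calculation, and I use two arms of 16 below. The documents give no sample-size figure for the symptom score.

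**2. Inputs for the symptom score.** n = 16 per arm comes from Section 10.0a. The SD and the pre/post correlation r are not given. Results are therefore in SD units, and r is an assumption shown at 0.3, 0.5 and 0.7.

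**3. One pre-dose score as an ANCOVA covariate.** Variance factor relative to no adjustment = (1 − r²) × [1 + 1/(2n − 4)]. The second term is the small-sample cost: 1 + 1/28 = 1.036. The equivalent unadjusted size is 16 divided by the factor. Detectable differences and power use the noncentral t with 30 df (unadjusted) or 29 df (adjusted).

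| Analysis | Variance factor | Like n per arm, unadjusted | Detectable difference, 80% power | Power for an assumed 0.8 SD effect |
|---|---|---|---|---|
| No baseline | 1 | 16 | 1.024 SD | 59% |
| r = 0.3 | 0.91 × 1.036 = 0.94 | 17 | 0.995 SD | 62% |
| r = 0.5 | 0.75 × 1.036 = 0.78 | 21 | 0.903 SD | 70% |
| r = 0.7 | 0.51 × 1.036 = 0.53 | 30 | 0.745 SD | 85% |

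The detectable difference with one baseline equals the unadjusted one at r of about 0.19. Below that, adjustment costs slightly more than it returns.

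**4. Mean of two pre-dose scores.** If all pairs of scores share the same correlation r (a further assumption), the squared correlation with the mean of two is 2r²/(1 + r): 0.138, 0.333 and 0.576. The detectable difference becomes 0.968, 0.852 and 0.679 SD, with power 64%, 75% and 91% for 0.8 SD.

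**5. Size of chance imbalance.** The baseline difference between arms has SD √(2/16) = 0.35 patient SDs. Only r times that carries into the outcome comparison, about 0.18 SD at r = 0.5. This is the same variance that step 3 removes, not an additional loss.

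**6. Does Table 1 supply a baseline?** Its blood-draw line (kallikrein-kinin markers and pharmacokinetics) is also undated, yet Appendix A gives Days -7 and 13 clinical laboratory samples only. An undated line in Table 1 therefore does not mean every dialysis visit. It leaves a conflict to resolve and does not establish a pre-dose score.

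**7. Which session does a score describe?** The Study protocol text asks at the end of the session. The Symptoms questionnaire subsection asks at the next regular session. The first dose is given on a non-dialysis day, so under the second rule the Day 1 form would describe a session before dosing.

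**8. Is there an outcome in the stated window?** Counting from the first dose, the second week has no scheduled questionnaire: nothing falls between Day 3 and Day 15. Day 13 is a dialysis visit with a blank cell. Under the next-session rule the Day 15 form might describe the Day 13 session, but the plan does not say so.

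**The case against.** The strongest reply is that nothing here is invalid. Randomisation protects the comparison, the confidence interval already allows for chance imbalance, and the score is one of several secondary endpoints with no power claim. All of that stands, and it limits the point to efficiency. A reader might infer that a missing baseline biases the result, or that imbalance passes in full into the treatment effect. The documents do not support either reading (step 5).

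A reader might also infer that no pre-dose score can exist. That is too strong: undated Table 1 can be read as covering Days -7 and -1, and under the next-session rule the Day 1 form might describe a pre-dose session. Neither is designated as a baseline, however, and the dated schedule and the narrative both point the other way.

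The gain also depends on a correlation that the documents do not give. At 0.3 it is only about 6% of the variance, and it could be nil.

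Two further replies carry less weight. Eligibility requires symptomatic episodes, but a qualifying history is not the 0 to 4 score. Section 10.0b allows covariates, but in the mixed model for blood pressure, with none named.

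The Appendix A row also covers the blood pressure log. I make no point there: Section 6.0 already measures blood pressure on dialysis study days and draws on clinic logs.

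**Conclusion.** The point holds as a cheap gain in precision for a secondary endpoint that is central to Aim 2. As scheduled, the symptom score has no designated baseline, and Appendix A, Table 1 and the text must be reconciled. With one pre-dose score the variance falls by about 6%, 22% or 47% at r of 0.3, 0.5 or 0.7. Two averaged scores gain somewhat more. These figures assume 16 analysed per arm, a linear pre/post relation and a correlation that the documents do not give. They say nothing about the primary blood pressure endpoint. The gain is realised only if the analysis changes too: a parallel design has no lanadelumab-placebo pairs, so the planned paired test cannot use the baseline.

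**What to change.** 1. Give the symptoms questionnaire on Days -7 and -1, and tick both in Appendix A.
2. Align Appendix A, Table 1 and the Study protocol text, including the blank Day 13 cell. State which days supply the second-week endpoint in Section 10.0a.
3. State which dialysis session each score describes, and use one rule in both the Study protocol and Symptoms questionnaire subsections.
4. In Section 10.0b, replace the paired t-test for this endpoint with a two-arm ANCOVA or mixed model, with each patient's mean pre-dose score as a prespecified covariate.

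The cost is a few minutes of questionnaire time at two visits that already take place, one degree of freedom, and edits to the schedule and analysis text. No extra visit or staff is needed. If the true correlation is below about 0.19, one baseline score would bring no gain and a very small loss: at zero correlation the detectable difference is 1.043 SD instead of 1.024.
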